## 8.2 Safety Assessments

This study aims to understand how sleep deficiency influences youth's ability to engage with, implement, and benefit from a pain self-management intervention. We will study a cohort of 80 youth, ages 12 to 17 years, with chronic musculoskeletal, head, or abdominal pain. Assessments will occur at baseline, immediately after intervention, and repeated at 3 months post-intervention. Mediators will be assessed at an additional mid-treatment (4 weeks) data point. All youth will receive an internet-delivered pain self-management intervention (WebMAP) over an 8-week period. Following the recommended Common Data Elements for self-management we measure three self-management processes including patient activation, pain self-efficacy, and self-management skills, and assess patient-reported outcomes of health (global health, fatigue) and pain (pain symptoms, pain-related disability). Positive and negative affect will be assessed as potential mediators. Sleep deficiency will be comprehensively assessed with subjective measures, daily sleep logs, and ambulatory actigraphy monitoring to measure disrupted sleep, amount of sleep, sleep quality, and insomnia symptoms. The risks of this intervention are well known from prior studies using this intervention, and they are minimal. Participants will receive their usual medical treatment during the study and thus will be monitored by their treating physicians. Given this study profile, we propose the following Data and Safety Monitoring Plan which has been approved by our Institutional Review Board (approval date: 4/19/18).

We will of course comply with any additional requirements or changes to the plan that the National Institute of Nursing Research (NINR) request prior to the study initiation.

### **2. Procedures for monitoring study safety, minimizing research-associated risk, and protecting confidentiality**

**Monitoring study safety:** Monitoring study safety will occur from the initial screening, throughout the informed consent process, and through study completion. Weekly monitoring of participants and internal monthly quality audits for compliance with IRB requirements, conformance with informed consent requirements, verification of source documents, and investigator compliance. The PI will report all serious and/or unexpected adverse events to the IRB, the SMC, and the NINR within 48 hours after identification.

The PI will be responsible for the day-to-day trial management of this study. The Clinical Research Associate and Psychology Fellow, under the PI's supervision, will use an Access database checklist to ensure that all study procedures are being followed (including consents) and that all surveys are being completed according to schedule. Study staff will log onto the administrative website of the intervention program each day to review study participant data and to download their study assessments. The PI will monitor for the responses that are spontaneously reported by children or parents. In the case of critical event, the PI (or a designated covering investigator, if [name] is not available) will stop the intervention and will be available 24 hours a day to be called via cell phone to address questions. These are reviewed immediately with the clinically responsible PI and/or Co-I. All actions taken will be documented on a case report form.

**Minimizing research-associated risks:** Meticulous monitoring of study safety will be conducted by the PI ([name]), Co-Investigators, and the Safety Monitoring Committee. All appropriate steps will be taken to maintain the security of participant data. All participant raw data will be coded and stored separately from identifying information on a password protected server to which only study staff has access. Online data will be saved in a secure password protected database that is protected by the highest standards for electronic data safety. The data stored on the central server will be automatically coded with participant ID and no personal identifiers will be associated with these data. Study personnel will be able to access the data on the central server using a login and password in order to track compliance.

The occurrence of any adverse event will be assessed weekly at study meetings. Study personnel will review the event forms from the previous week for events that were reported as new. The investigators will follow all adverse events until the point of a satisfactory resolution. Study safety, risk and reports of other problems (issues not meeting criteria for a serious adverse event) will be reviewed at quarterly meetings with the PI, Co-Investigators, and an action plan to address any identified issue will be developed and monitored by the Safety Monitoring Committee. The PI will comply with all requirements of the IRB for the reporting of safety data and adverse/serious adverse events. The PI will report all serious and/or unexpected adverse events to the IRB, the SMC, and the NINR within 48 hours after identification. The PI will provide a discussion of any adverse events occurring in the course of the study to the IRB on an annual basis. All adverse events experienced by study participants from the date of enrollment through the completion of the study will be reported. All adverse events regardless of attribution to treatment procedures will be collected and recorded. Participants will be asked in an open-ended way about the presence of any adverse events. The likelihood that the event is related or not related to treatment will be noted.

Protection of confidentiality of participants' data: Data quality will be ensured by having trained staff demonstrate compliance with study protocol to include auditing selected cases (10%) for compliance with IRB requirements, conformance with informed consent requirements, verification of source documents, and investigator compliance with all human subjects and HIPAA requirements. Data quality will also be ensured by having each completed survey checked to minimize missing data. The Research Associate will also keep track of reasons for missing data in the Access database. In order to have the most complete data for analysis, a benchmark of success will be to have complete data on >95% of subjects retained to study completion.

Errors in data capture, entry and analysis will be greatly reduced by the use of REDCap which alerts the participant and research staff to missed or implausible questionnaire responses. REDCap also provides output results into a file easily imported into SPSS, where SPSS syntax can autoscore the questionnaire responses, greatly reducing scoring errors. All data manipulation is recorded by REDCap. It is standard procedure in the PI's laboratory that all data manipulation and transfer is always double checked by another research staff member, who is required to sign off on the double check. We also note that the Office of Research Compliance at Seattle Children's Hospital audits all research studies at least once, and PIs and research staff are continually educated on research best practices.

The Web-based electronic data management system is password protected and encrypted, no direct identifiers will be present among electronic data. The code that links identifying information will be accessible only to study staff and will be kept in a locked office in a locked file, separate from data collected during the course of the study and separate from the link between study data and subject identity. Confidentiality of research data will be protected as described in the Human Subjects' Section of the Application.

### **3. Procedures for identifying, reviewing, and reporting adverse events and unanticipated problems:**

The PI will comply with all requirements of the IRB for the reporting of safety data and adverse/serious adverse events. The PI will report all serious and/or unexpected adverse events to the IRB, the SMC, and the NINR within 48 hours after identification. In the event that a subject withdraws from the study or the investigator decides to discontinue a subject due to a serious adverse event, the subject will have appropriate follow-up monitoring until the problem has resolved or stabilized or is determined to be unrelated to the study.

The SMC will review all adverse events and unanticipated events within 48 hours and will discuss them to determine the likelihood that the serious adverse event is related to involvement in the research. They will also review all study-related data on a semi-annual basis in a safety monitoring meeting to review information related to the safety of study participants and summarize any adverse events.

[name], as PI, will provide timely reporting to the funding agency of: any unanticipated problems or serious adverse events that may be related to the study protocol; any IRB-approved revisions to the

study protocol that change the risk for participants; any action taken by the IRB regarding the research activity and any response to those actions; and a summary of recommendations made by the safety monitoring committee and any action plan for response.

Additionally, all adverse events, serious and non-serious, and unanticipated problems as defined in the HHS guidance (<http://www.hhs.gov/ohrp/policy/advevntguid.html>), will be reported annually to the IRB during the yearly renewal processes. The PI will generate and submit to the above entities a report that will be masked to minimize inclusion of information that can link the event to a specific person.

**d. For multisite studies, procedures to ensure compliance with the monitoring plan and reporting requirements across study sites.**

NA. This is not a multi-site trial

**e. An assessment of external factors that may have an impact of the safety of participants or on the ethics for the research study**

The research procedures and treatment involve minimal risk. [name] keeps abreast of the literature and attends scientific meetings to stay informed of developments in pain and sleep treatments in children to learn about factors that may change the identified risks or possible benefits to participants. In the unlikely event that new information that might alter the risk of research procedures is learned, [name] will revise the protocol to minimize such risks and inform the IRB, SMC, and NINR. In addition, the participants will be notified of any significant new findings that develop during the course of research that may affect their wish to continue participation in the study.

**f. The advanced plans for interim and/or futility analysis**

Given the small scope of the study, and to preserve the statistical power, interim and/or futility analysis is/are not planned.

## 8.3 Adverse Events and Serious Adverse Events

### 8.3.1 Definition of Adverse Events

An adverse event is any untoward or unfavorable medical occurrence in a human subject, including any abnormal sign (for example, abnormal physical exam or laboratory finding), symptom, or disease, temporally associated with the subject's participation in the research, whether or not considered related to the subject's participation in the research.

### 8.3.2 Definition of Serious Adverse Events

A serious adverse event (SAE) is one that meets one or more of the following criteria:

- Results in death
- Is life-threatening (places the subject at immediate risk of death from the event as it occurred)
- Results in inpatient hospitalization or prolongation of existing hospitalization
- Results in a persistent or significant disability or incapacity

- Results in a congenital anomaly or birth defect
- An important medical event that may not result in death, be life threatening, or require hospitalization may be considered an SAE when, based upon appropriate medical judgment, the event may jeopardize the subject and may require medical or surgical intervention to prevent one of the outcomes listed in this definition.

### 8.3.3 Classification of an Adverse Event

To assess relationship of an event to study intervention, the following guidelines are used by the Co-PIs:

1. Related (Possible, Probable, Definite)
  - a. The event is known to occur with the study intervention.
  - b. There is a temporal relationship between the intervention and event onset.
  - c. The event abates when the intervention is discontinued.
  - d. The event reappears upon a re-challenge with the intervention.

#### 2. Not Related (Unlikely, Not Related)

- a. There is no temporal relationship between the intervention and event onset.
- b. An alternate etiology has been established.

### 8.3.3.1 Severity of Event

The following scale will be used by the Co-PIs to grade adverse events:

1. Mild: no intervention required; no impact on activities of daily living (ADL)
2. Moderate: minimal, local, or non-invasive intervention indicated; moderate impact on ADL
3. Severe: significant symptoms requiring invasive intervention; subject seeks medical attention, needs major assistance with ADL

### 8.3.3.2 Relationship to Study Intervention/Experimental Manipulation

To assess relationship of an event to study intervention, the following guidelines are used by the Co-PIs:

1. Related (Possible, Probable, Definite)
  - a. The event is known to occur with the study intervention.
  - b. There is a temporal relationship between the intervention and event onset.
  - c. The event abates when the intervention is discontinued.
  - d. The event reappears upon a re-challenge with the intervention.
2. Not Related (Unlikely, Not Related)
  - a. There is no temporal relationship between the intervention and event onset.
  - b. An alternate etiology has been established.

### 8.3.3.3 Expectedness

The study PIs will be responsible for determining whether an SAE is expected or unexpected.

An adverse event will be considered unexpected if the nature, severity, or frequency of the event is not consistent with the risk information previously described for the intervention.

## 8.4 Unanticipated Problems

Unanticipated problems involving risk to human subjects will be recorded and reported throughout the entire study.

The Office for Human Research Protections (OHRP) considers unanticipated problems involving risks to subjects or others to include, in general, any incident, experience, or outcome that meets all of the following criteria:

- unexpected in terms of nature, severity, or frequency given (a) the research procedures that are described in the protocol-related documents, such as the IRB-approved research protocol and informed consent document; and (b) the characteristics of the subject population being studied;
- related or possibly related to participation in the research (“possibly related” means there is a reasonable possibility that the incident, experience, or outcome may have been caused by the procedures involved in the research); and
- suggests that the research places subjects or others at a greater risk of harm (including physical, psychological, economic, or social harm) than was previously known or recognized.

## 9 STATISTICAL CONSIDERATIONS

### 9.1 Statistical Hypotheses

- Primary Objective:

**Aim 1. Characterize the relationship between baseline sleep deficiency and self-management processes.** H1. Greater baseline sleep deficiency (shorter sleep duration, poorer sleep quality, increased insomnia symptoms, greater wake time after sleep onset) will be associated with lower activation, lower pain self-efficacy, and lower use of self-management skills from pre- to post-treatment. H2. Positive and negative affect and executive functioning will mediate the relationship between sleep deficiency and self-management processes.

- Secondary Objective:

**Aim 2. Determine the effect of baseline sleep deficiency on treatment acceptability, engagement, and benefit from an internet-delivered pain self-management intervention.** H3. Greater sleep deficiency will be associated with lower perceptions of treatment acceptability and engagement (fewer logins, fewer completed treatment modules and assignments). H4. Greater sleep deficiency will be associated with less benefit (fewer improvements) in ratings of global health, fatigue, pain symptoms, and pain-related disability following pain self-management intervention. H5. Positive and negative affect and executive functioning will mediate the relationship between sleep deficiency and treatment acceptability, engagement and benefit.

### 9.2 Sample Size Determination

Aim 1: A series of Monte Carlo simulations were conducted to evaluate longitudinal mediation (70). Results indicate 80% power for a sample size of 75 given a mediated effect of approximately 27% or larger and specific indirect effects of  $R^2 = .12$  or larger.

Aim 2: A series of Monte Carlo simulations were specified (27) to evaluate power to detect variance in linear change. Results indicate a sample size of 52 is needed. Adding predictive structural paths to the simulated LGMs indicated that a sample size of  $N = 75$  would be powered at .80 to detect an effect size as small as  $R^2 = .06$  and .03 for the slope and intercept, respectively (71).

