### 5.5 Strategies for Recruitment and Retention

1. Our target sample size includes 80 adolescents ages 12-17 of any sex, race and ethnicity. Based on the percentage of eligible participants in previous studies with similar criteria, we anticipate that we will need to screen 100 participants in order to reach our target sample size of 80 adolescents.

a. Regarding the NIH Policy and Guidelines on The Inclusion of Women and Minorities as Subjects in Clinical Research:

i. Our sample will include female children/adolescents and mothers or female caregivers. We anticipate a large proportion of child and caregiver participants to be female – in previous studies with a similar population, 74% of child participants and 90% of parent participants were female.

ii. Our sample will include minorities. Specifically, we estimate enrolling participants at the following rate: 11.0% Hispanic/Latino and 89.0% not Hispanic/Latino. In terms of racial categories, we expect to enroll participants in the following proportions: 78.4% White, 7.0% Asian, 4.0% More than One Race, 9.0% Black or African American, 1.4% American Indian/Alaska Native, and 0.2% Native Hawaiian or Other Pacific Islander. Referrals will come from the Seattle Children's Pain Clinic.

iii. Participants will be recruited via referral from providers at Seattle Children's Pain Clinic and via EMR review. Health care providers will inform patients and families about the study and provide families with study information in the form of a flyer. Providers will then ask families if they are willing to be contacted by research staff to assess interest in the study and discuss participation. The provider will refer interested, potentially eligible participants by entering participant and parent names and contact information into a secure REDCap database hosted at SCH, or may send the referral by secure fax, email, or voicemail. Families who do not give permission for their information to be shared with SCH by the referral site may still contact SCH staff or submit their information to SCH via a secure link on the study website (self-referral), or via email or secure voicemail.

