### 9.3 Statistical Analyses

Data will be reviewed for completeness and errors including consistency checks for relevant variables. Tabular and graphical methods of data exploration including frequency tables, scatterplots, and box plots will be used to explore distributions of study variables. For the primary analytic plan, we will rely

on panel and latent growth models (LGM), within the structural equation modeling (SEM) framework (55-57). Both approaches can be implemented within a manifest and/or latent variable context (58). Unlike traditional repeated-measures analysis of variance, SEM allows for a more accurate and flexible approach to analyzing repeated measures data by simultaneously modeling change in the means (fixed effects) and in the variance and covariance of initial level and change (random effects) (56, 59-61). We include biological covariates of age, sex, and pain location in all models. We expect 10% attrition for a final projected sample size of  $n = 72$ . Full Information Maximum Likelihood (FIML) estimation will be used to handle missing data related to attrition and non-response (62) incorporating robust standard errors or bootstrapping to correct for non-normality (61). FIML estimation improves accuracy and power relative to other missing data handling methods (63, 64).

**Aim 1. Characterize the relationship between baseline sleep deficiency and self-management processes.** We will use structural equations (65, 66) to assess interrelations, direct effects, and indirect mediation effects in a longitudinal panel model. Mediation will be tested by decomposing a total effect of each sleep deficiency measure (duration, wake time, quality, insomnia symptoms) on self-management processes into direct effects and indirect effects (65, 66). Significance tests of indirect effects will be carried out using the Monte Carlo (*empirical-M*) method to obtain 90% asymmetric confidence intervals (67-69).

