Expected Results, Interpretation, and Possible Pitfalls. We expect the higher the level of sleep deficiency the higher negative affect, lower positive affect, *lower executive functioning*, lower the behavioral activation, self-efficacy, and self-regulation at baseline. There will likely be an indirect effect of sleep deficiency on affect *and executive function* and of affect *and executive function* on self-management processes. *We also expect that a significant indirect effect will indicate that sleep deficiency affects change in self-management processes by influencing affect or executive function.*

**Aim 2. Determine the effect of baseline sleep deficiency on treatment acceptability, engagement with, and benefit from an internet-delivered pain self-management intervention.** We will use LGMs to model individual differences in final acceptability and engagement status and the rates of change in global health, pain symptoms, fatigue, and pain-related disability (56, 59-61) and to test the proposed predictive and mediated effects.

Expected Results, Interpretation, and Possible Pitfalls. We expect that global health will improve over the course of the study while pain, fatigue, and pain-related disability will decrease. We also expect that participants will significantly vary around the average intercept and slope. We expect the higher the initial level of sleep deficiency the shallower the increase in global health over time and the shallower the decline in pain, fatigue, and pain-related disability. Across all models we expect less than 10% attrition over the course of the study based on our prior work (27). We will use the maximum likelihood estimation option in the Mplus 7.3 software program to deal with missing data and use the robust standard error option to correct for non-normality (61).

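### Section 9.2 states 80% power at N = 75 for both aims, but 80 enrolled with the plan's own 10% attrition leaves 72, so the stated power is not supported at the projected sample size

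*Combined protocol and SAP*

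**What the plan says.** - **Power (9.2).** Aim 1: "Results indicate 80% power for a sample size of 75 given a mediated effect of approximately 27% or larger". A second condition is attached: each specific indirect effect must reach an R² of at least .12. Aim 2: N = 75 gives power .80 for R² = .06 on the slope and .03 on the intercept.
- **Enrolment (5.5).** "Our target sample size includes 80 adolescents ages 12-17". Section 4.4 repeats the target of 80.
- **Attrition (9.3).** "We expect 10% attrition for a final projected sample size of" 72. Later in the same section: "Across all models we expect less than 10% attrition over the course of the study".
- **Analysis (9.3).** Missing data are handled by FIML. Age, sex and pain location enter every model. Indirect effects are tested by a Monte Carlo method "to obtain 90% asymmetric confidence intervals".
- **Mediators (9.1, H2).** "Positive and negative affect and executive functioning will mediate the relationship between sleep deficiency and self-management processes".

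Section 9.2 does not report the number of mediators simulated, the path values, the correlations between mediators, the covariates, the missing-data pattern or the interval level.

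**The concern.** The power statements and the attrition projection sit in adjacent sections and use different sample sizes. Section 9.2 speaks of 75 youth without saying whether that means enrolled, retained or an effective number. Section 9.3 then projects 72. If 75 means youth with outcome data, the plan falls 3 short of the sample on which its power rests, for both aims.

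Aim 1 is the primary objective, and H2, the mediation hypothesis, is part of it. The 80% is what a later reader would use to weigh a null result, so it should describe the sample the trial expects to have. Because the simulation inputs are not reported, that reader cannot adjust the figure.

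**Working it through.** **Step 1. Sample size.** Inputs: 80 enrolled (5.5), 10% attrition (9.3), N = 75 (9.2).

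- Projected final n: 80 × 0.90 = 72, as 9.3 states.
- Shortfall: 75 − 72 = 3.
- Attrition at which 75 is just kept: 1 − 75/80 = 6.25%, or 5 youth.
- Enrolment that would leave 75 at 10% loss: 75/0.90 = 83.3, so 84.
- Losing 6 or 7 of 80 (7.5% or 8.75%) satisfies the looser statement of under 10% but leaves 74 or 73.

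**Step 2. Can the 80% be reproduced?** Only under assumptions, since 9.2 does not say which path R² = .12 refers to. The check used a simplified model with observed variables (sleep → mediator → outcome), a = b = √.12, a Monte Carlo interval for a·b and 10,000 replicates. To honour the 27% input, the direct effect was set so that a·b is 27% of the total: .12/.27 − .12 = 0.324. Covariate terms were assumed unrelated to the other variables.

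| Reading (one mediator) | N = 75 | n = 72 |
|---|---|---|
| 90% interval, no direct effect | 0.817 | 0.797 |
| 90% interval, 27% mediated | 0.868 | 0.852 |
| 95% interval, 27% mediated | 0.777 | 0.755 |
| 95% interval, no direct effect | 0.710 | 0.686 |
| 90% interval, no direct effect, four covariate terms | 0.793 | 0.770 |

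Two readings come within 2 points of 0.80 at N = 75: the 90% interval with no direct effect, without covariates and with four covariate terms. Neither uses the 27% input. The documents do not give enough to confirm or refute the 80%. The stable result is the difference between the columns: 1.6 to 2.4 points.

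**Step 3. Loss if the 80% is taken as exact at 75.** For a Wald-type test, power at 72 = Φ[(z₁₋α/₂ + z₀.₈₀) × √(72/75) − z₁₋α/₂].

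- α = .05: (1.960 + 0.842) × 0.980 = 2.745; 2.745 − 1.960 = 0.785; power 0.784.
- α = .10 (the 90% interval): (1.645 + 0.842) × 0.980 = 2.436; 2.436 − 1.645 = 0.791; power 0.786.
- Simulation with a = b = 0.34, which gives 0.800 at 75: 0.781 at 72.

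Put the other way, the R² needed for the same power grows by roughly 75/72 = 1.042, so .12 becomes about .125 and .06 about .0625.

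**Step 4. What FIML recovers.**

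- *Aim 1, best case.* All 80 contribute to the sleep-to-mediator path and 72 to the outcome path: 0.819, against 0.817 for a complete 75 (90% interval, no direct effect, no covariates). The gap closes.
- *Aim 1, half of the losses before the mediator visit.* 0.809, against 0.816 for a complete 75 in the same set of runs. The gap closes in part.
- *Aim 2, slope effect.* The information from 80 enrolled with 8 lost equals that from 72.0 to 74.4 complete youth. Assumptions: losses before the post-treatment visit and before the last visit split 0/8, 4/4 or 8/0; intercept–slope correlation −0.3 to 0.3; error variance 0.25 to 1.0. It stayed below 75 in every setting tried.

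**The case against.** The strongest reply is that the mismatch has almost no consequence. Two points of power would not change how a null result is read in a single-arm mechanism study of 80 youth. FIML keeps partly observed participants, and mediators have an extra assessment at 4 weeks, before much attrition could occur; in the favourable case Aim 1 loses nothing. H1 is framed from pre- to post-treatment, so later losses do not all bear on it, although 9.3 fits a longitudinal panel model and section 3 schedules Aim 1 measures at 6 months as well. Section 9.3 also says attrition will be under 10%. Under a reading that uses the 27% input with a 90% interval, power is above 0.80 even at 72.

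Most of this stands, and it limits the size of the point. It does not make 75 the projected sample: attrition under 10% restores 75 only at 6.25% or less, and FIML's recovery depends on when youth are lost, which the plan does not state.

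A reader might draw two stronger inferences that the documents do not support.

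- *That the stated power is not delivered.* The 80% can be neither confirmed nor refuted from 9.2, and FIML may close the gap for Aim 1.
- *That H2's three mediators push power lower still.* The plan does not say they are fitted jointly. Its plural reference to specific indirect effects suggests that several mediators may already be in the simulation. Section 8.1 describes the two affect scales as uncorrelated and gives no correlation for executive functioning. In trial calculations with three mediators fitted together at n = 72 (90% interval, assumed residual correlation 0 to 0.4), power per specific effect ran from 0.376 to 0.912. The result depended on the assumed correlation and on whether R² = .12 describes a mediator's unique effect or its effect when fitted alone. The upper values require the mediators to explain 45% to 70% of outcome variance, a strong premise, but nothing in the documents rules on it. The direction is open, and no three-mediator figure should be asserted.

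**Conclusion.** The point holds as a mismatch between 9.2 and the plan's own projection. Power for both aims is stated at N = 75, while 80 enrolled with 10% lost gives 72. This part is arithmetic from the documents and needs no assumption.

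Its size is modest: about 0.78 at 72 if power is exactly 0.80 at 75, a loss of about 2 points. That rests on complete records at 72. Under FIML the loss is smaller and, for Aim 1 at best, nil; for the Aim 2 slope some shortfall remained in every setting examined. All simulated figures come from a simplified model, not from the planned panel or growth models.

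The correct conclusion is that the stated 80% is not supported at the projected sample size, not that the trial is underpowered.

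**What to change.** Rerun the existing Monte Carlo simulations for both aims with 80 enrolled and 10% lost (n = 72 at the last visit), analysed under FIML. Include age, sex and pain location, the mediators as they will be fitted, and, for indirect effects, the 90% interval that 9.3 specifies. Replace the N = 75 statements in 9.2 with the resulting power, or with the effect detectable at 80%.

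In the same sentences, state the number of mediators, the path values and what R² = .12 refers to, the assumed mediator correlations and the timing of losses. That lets a reader check the figure and answers the three-mediator question from the investigators' own model. Use one attrition figure throughout 9.3.

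The cost is a rerun of existing simulations and a short edit to 9.2. Enrolment and the analysis are unchanged. The downside is that the stated figure may be slightly less favourable.
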